### **4.3. Exposure to Study Drug**

#### **4.3.1. Extent of Exposure and Treatment Compliance**

Subjects were trained by study personnel on how to self-administer study drug with the abaloparatide-SC injection pen or the abaloparatide-sMTS patch. On the days of study site visits, study drug must be administered at the study site to accommodate pre-administration and post-administration procedures.

The overall duration of study drug exposure will be calculated using the data recorded on the eCRF as follows:

- Overall duration of study drug exposure (days) = (date of last dose – date of first dose) + 1.

If the date of last dose is missing, then the earlier of the following 2 dates will be used as the last dose date for analysis and summary purposes: the final visit/early termination visit date or the last drug dispense date + 30 days.

For the abaloparatide-SC group, the total number of doses delivered and study drug administration compliance will be calculated in two ways as follows:

- **Based on missed doses in subject diary:**
  - Number of doses delivered = Overall duration of study drug exposure – Total number of missed doses per subject diary
  - Percent compliance (%) to study drug administration =  $(\text{Number of doses delivered} / \text{Overall duration of study drug exposure}) \times 100\%$
- **Based on measurement of drug remaining in pen:**
  - Number of doses delivered =  $[(45.5 \text{ mm} \times \text{Number of used pens}) - \text{Sum of measurements of drug remaining in all used pens}] / 1.08 \text{ mm}$ . Here the 45.5mm is the initial measurement of unused study drug in an unused injection pen and 1.08mm is the distance the plunger travels for each 80 ug dose from the pen.
    - Note: If the measurement of drug remaining in any used pen is missing, then 100% compliance will be assumed for the intended treatment period for which the pen with missing measurement of drug remaining was dispensed. For each pen dispensed prior to Month 11 visit, the intended treatment period is a 30-day period starting from the day when first dose was taken from the pen. For the pen dispensed at Month 11 visit, the intended treatment period is a period less than or equal to 30 days starting from the day when first dose was taken from the pen to the EOT day. The number of doses taken from the pen with missing measurement of drug remaining is a value less than or equal to 30, which will be based on the number of doses taken from the pen(s) with non-missing measurement of drug remaining and the duration of the treatment period. The number of doses delivered would be the minimum of the following:
      - Total doses taken from pens with non-missing measurements of drug remaining (calculated as:  $[45.5 \text{ mm} \times \text{Number of pens with non-missing measurements of drug remaining} - \text{Sum of measurements of drug remaining from all pens with non-missing measurements of drug remaining}] / 1.08 \text{ mm}$ ) +  $30 \times \text{number of pens with missing measurement of drug remaining}$
      - Overall duration of study drug exposure (last dose date - first dose date + 1)
    - Percent compliance (%) to study drug administration =  $(\text{Number of doses delivered} / \text{Overall duration of study drug exposure}) \times 100\%$

For the abaloparatide-sMTS group, the total number of doses delivered and study drug compliance will be calculated in two ways as follows:

- **Based on missed doses in subject diary:**
  - Number of doses delivered = Overall duration of study drug exposure - Total number of missed doses per subject diary
  - Percent compliance (%) to study drug administration =  $(\text{Number of doses delivered} / \text{Overall duration of study drug exposure}) \times 100\%$
- **Based on number of patches returned:**
  - Number of doses delivered =  $20 \times \text{Number of kits dispensed} - \text{Sum of patches returned in all dispensed kits}$ . The number of patches dispensed per kit is 20.

- Note: If the number of patches returned in any dispensed kit is missing, then 100% compliance will be assumed for the treatment period for which the unreturned kit was dispensed. The number of patches used from the unreturned kit is a value less than or equal to 20, which will be based on the number of patches used from the returned kit(s) dispensed at the same visit as the unreturned kit. The number of doses delivered would be the minimum of the following:
  - Total patches taken from kits with non-missing number of patches returned (calculated as:  $20 \times \text{Number of non-missing kits} - \text{Sum of number of patches returned from all non-missing kits}$ )  $+ 20 \times \text{number of kits with missing number of patches returned}$
  - Overall duration of study drug exposure (last dose date - first dose date + 1)
- Percent compliance (%) to study drug administration =  $(\text{Number of doses delivered} / \text{Overall duration of study drug exposure}) \times 100\%$

The duration of study drug exposure, duration category in months ( $\leq 1$  month,  $1 < \text{to } \leq 3$  months,  $3 \text{ to } \leq 6$  months,  $6 \text{ to } \leq 9$  months, and  $> 9$  months), number of doses delivered, and percent compliance to study drug administration will be summarized by treatment group for the Safety, mITT and PP populations. The summaries will not be provided for the ITT population since the Safety and ITT populations represent the same subjects with respect to study drug exposure.

The study drug exposure and compliance will also be summarized by region (North America and Europe) for the Safety, mITT and PP populations.

To evaluate the relationship between study drug exposure and the antibody status, the duration of study drug exposure and percent compliance to study drug administration will also be summarized by antibody status (ADA-, ADA+/Nab+, ADA+/Nab-, All ADA+, and Overall) using the Antibody Population.

Two different patches will be dispensed to subjects in the abaloparatide-sMTS group. The ultra-low bioburden patches will be dispensed from Day 1 to all subjects. Sterile patches (the patches intended for commercial use) will be dispensed to subjects after confirmation that the sterile product is bioequivalent to the ultra-low bioburden product (Study 058-05-023). For the abaloparatide-sMTS group, the duration of study drug exposure, duration category in months, number of doses delivered and percent compliance with study drug administration using two calculations of percent compliance will also be summarized by patch type (ultra-low bioburden, sterile) for the Safety, mITT and PP populations.

If a subject is shown to be  $<80\%$  compliant with study drug administration using both calculations of study drug administration compliance for abaloparatide-sMTS group, or is  $<80\%$  compliant with study drug administration using both calculations of study drug administration compliance for the abaloparatide-SC group, this subject will be considered as having a critical protocol deviation and thus excluded from the PP Population.

Subjects' drug exposure and compliance will be carefully reviewed against the onset of the COVID-19 pandemic. Each subject's study drug exposure and compliance prior to 01 March 2020 and on or after 01 March 2020 will be calculated based on information collected from the subject diary:

- For subjects with last dose date prior to 01 March 2020 and subjects with first dose date on or after 01 March 2020, their duration of study drug exposure (days), number of doses delivered, and percent compliance to study drug administration relative to 01 March 2020 will be calculated as above based on the missed doses in subject diary
- For subjects who started taking the study drug prior to 01 March 2020 and continued on or after 01 March 2020, their duration of study drug exposure and compliance before 01 March 2020 and on or after 01 March 2020 will be calculated as follow:
  - Durations of study drug exposure relative to 01 March 2020:
    - Duration before 01 March 2020 = 29 February 2020 – date of first dose + 1
    - Duration on or after 01 March 2020 = Overall duration of study drug exposure – duration before 01 March 2020; where overall duration of study drug exposure = last dose date – first dose date + 1
  - The numbers of doses delivered relative to 01 March 2020 (The number of doses provided to a subject is different at each visit between the abaloparatide-SC group and abaloparatide-sMTS group. Therefore, different formulas are used to calculate the number of doses delivered before 01 March 2020 for the two treatment groups):
    - Number of doses delivered before 01 March 2020 (abaloparatide-SC group) =  $A - (B + [C \times \min \{1, D / E\}])$ , and will be rounded to the nearest integer; where:
      - A = Duration of study drug exposure before 01 March 2020
      - B = Total number of missed doses from pens dispensed before 01 March 2020 and with scheduled return date before or on 01 March 2020
      - C = Number of missed doses from pens dispensed before 01 March 2020 but with scheduled return date after 01 March 2020
      - D = 01 March 2020 – last drug dispensing date prior to 01 March 2020
      - E = First drug dispensing date on or after 01 March 2020 – last drug dispensing date prior to 01 March 2020
    - Note: if there is no drug dispense on or after 01 March 2020, then E = Last dose date - last drug dispensing date prior to 01 March 2020
  - Number of doses delivered before 01 March 2020 (abaloparatide- sMTS group) =  $A - (B + C \times D)$ , and will be rounded to the nearest integer; where:
    - A = Duration of study drug exposure before 01 March 2020
    - B = Total number of missed doses from kits dispensed before 01 March 2020 and with scheduled return date before or on 01 March 2020
    - C = Number of missed doses from kits dispensed during the last drug dispensing visit before 01 March 2020 but with scheduled return date after 01 March 2020
    - D =  $(01 \text{ March 2020} - \text{last drug dispensing date prior to 01 March 2020})/30$
  - Number of doses delivered on or after 01 March 2020 = Number of doses delivered during whole study – number of doses delivered before 01 March 2020.
- The percent compliance (%) to study drug administration relative to 01 March 2020:

- Percent compliance before 01 March 2020 = (Number of doses delivered before 01 March 2020 / Duration of study drug exposure before 01 March 2020) × 100%
- Percent compliance on or after 01 March 2020 = (Number of doses delivered on or after 01 March 2020 / Duration of study drug exposure on or after 01 March 2020) × 100%.

The study drug exposure and percent compliance to study drug administration before 01 March 2020 and on or after 01 March 2020 will be summarized by treatment group for the Safety, mITT and PP populations. Similar summaries will not be provided by patch type (ultra-low bioburden, sterile) since the switch from ultra-low bioburden patch to sterile patch for subjects in abaloparatide- sMTS group did not occur until after 01 March 2020.

The number (%) of subjects with any missed dose or dose interruption as recorded on the Dose Interruption Log eCRF will be summarized by treatment group, along with the reason(s) for missed/interrupted dose(s) for the mITT, PP, and Safety populations. If a subject reported a start date for the missed/interrupted dose but no corresponding start date for the resumption of study drug, the occurrence of the missed dose/dose interruption will not be included in the summary. The total number of days with missed/interrupted dose for each subject will be calculated and summarized by descriptive statistics and in the following categories: 1-7 days, 8-14 days, 15-28 days, >28 days by treatment group.

Study drug exposure and study drug administration compliance data will be listed by treatment (including patch type for abaloparatide-sMTS group), study site, and subject number.

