### **3. Other date imputations**

Any event with a partial date that requires imputation but has no specific imputation rule will be imputed as follows:

- If the day is missing, then impute the day as '01'
- If the month is missing, then impute the month as 'JUL'
- If the imputation of a start date causes the start date to be post the non-missing end date, then the start date will be imputed as the end date.
- If the imputation of a start date causes the start date to be prior to the start of treatment (but the event should happen post-baseline), then the start date will be imputed as "treatment start date + 1."
- Any date cannot be imputed past the date of death. When this happens, the date will be imputed as the date of death.

**Appendix B. Algorithm to Identify Critical Protocol Deviations that Exclude Subjects from the Per-Protocol (PP) Population**

The below algorithm outlines the criteria for identifying critical protocol deviations. Subjects with at least one of these critical protocol deviations will be excluded from the PP population.

- A. Deviations of subject eligibility (Inclusion/Exclusion criteria) that will result in exclusion from PP population (refer to the protocol for the complete text of each inclusion/exclusion criterion below):
  - 1. Inclusion Criterion #2: Less than 5 years postmenopausal.
  - 2. Inclusion Criterion #3: A BMD T-score outside the required range or fracture criteria not met.
  - 3. Exclusion Criterion #1: History of more than 4 spine fractures, mild or moderate, or any severe fractures.
  - 4. Exclusion Criterion #2: Presence of abnormalities of the lumbar spine that would prohibit assessment of spinal bone mineral density (BMD).
  - 5. Exclusion Criterion #3: Unevaluable hip BMD or subjects who have undergone bilateral hip replacement.
  - 6. Exclusion Criteria #4, #5, #6: Diseases and treatments affecting bone strength.
  - 7. Inclusion Criterion #5: Laboratory tests affecting the bone strength.
  - 8. Exclusion Criteria #16, #17, #18, #19, #20, #21, #22, #23, #24 and #26: Prior treatment with bone-acting agents within the specified time periods.
- B. Deviations of study drug administration that will result in exclusion from PP population:
  - 1. Duration of study drug exposure is less than 3 months (90 days)
  - 2. Compliance to study drug administration < 80%
- C. Deviations of efficacy measurements that will result in exclusion from PP population:
  - 1. Lumbar spine BMD is missing at baseline

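### A wholly or largely missing diary blocks per-protocol exclusion for low compliance, because days without a recorded miss count as doses taken and both measures must be below 80%

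*SAP*

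**What the plan says.** SAP 4.3.1 sets the denominator from dose dates: "Overall duration of study drug exposure (days) = (date of last dose – date of first dose) + 1". It then gives two compliance measures in each arm.

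- **Diary, both arms.** Doses delivered are exposure days minus "Total number of missed doses per subject diary".
- **Return count.** For SC, plunger travel in used pens is converted to doses, where "1.08mm is the distance the plunger travels for each 80 ug dose from the pen". For sMTS, returned patches are subtracted from those dispensed: "The number of patches dispensed per kit is 20".

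Missing returns have an explicit rule: "If the measurement of drug remaining in any used pen is missing, then 100% compliance will be assumed" for the period that pen was meant to cover, and unreturned kits are treated the same way. There is no rule for blank or lost diary pages.

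For PP, SAP 4.3.1 takes a subject who is below 80% "compliant with study drug administration using both calculations of study drug administration compliance for abaloparatide-sMTS group", with a parallel clause for SC, and says that "this subject will be considered as having a critical protocol deviation and thus excluded from the PP Population". Appendix B, item B.2, says only "Compliance to study drug administration < 80" (per cent). It names neither measure and does not say that both must fail. SAP 2.2 makes Appendix B the algorithm that determines critical deviations.

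**The concern.** The diary measure is built from recorded failures, not from recorded doses. An unkept page holds no recorded miss, so the formula scores that day as taken. Protocol 5.7 asks the subject to write the reason for missed dosing in her diary, so the measure relies on a poorly adherent woman documenting her own lapses.

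Requiring both measures to fail is reasonable when both are observed. When the diary is absent, a default score of 100% overrides a return count that was actually measured. Gaps are foreseeable: the COVID-19 impact categories in SAP 4.1 include missed visits, remote visits and missing data.

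At stake is what the PP set means. SAP 4.4.1.2 repeats the primary non-inferiority analysis in it as support for the mITT finding. If under-dosed women remain in it, PP is not the adherent set that a reader will take it to be.

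**Working it through.** The plan states no figure to reproduce here, so the check evaluates its own formulas. Inputs are 360 days of exposure (12 months of 30 days, SAP 1.2.1), the 80% threshold, 45.5 mm per unused pen, 1.08 mm per dose and 20 patches per kit (all SAP 4.3.1).

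**1. Recorded misses needed.** Diary % = (360 − recorded misses) / 360.
- 72 misses: 288/360 = 80.0%, not below the threshold.
- 73 misses: 287/360 = 79.7%, below it.
- No diary, so 0 recorded misses: 360/360 = 100%.

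**2. A 50% return count with no diary.**
- SC: 12 pens, 15 doses used from each. Drug remaining per pen is 45.5 − 15 × 1.08 = 29.3 mm. Doses = (12 × 45.5 − 12 × 29.3) / 1.08 = 194.4 / 1.08 = 180, and 180/360 = 50%.
- sMTS: 24 kits (assuming two per 30 days), 300 patches returned. Doses = 20 × 24 − 300 = 180, again 50%.

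The diary measure is 100% in both cases, so the rule in SAP 4.3.1 is not met and she stays. No lower return count changes this. Setting the diary value to missing without changing the rule would not help, because *both below 80%* still could not be met.

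**3. Partly missing diaries.** Let a be true adherence and m the missing share of the diary. Assume that misses are spread evenly and that every miss on a kept page is recorded. Then diary % = 1 − (1 − a)(1 − m), which reaches 80% when m ≥ 1 − 0.20/(1 − a).

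| True adherence a | Smallest missing share m that keeps her in PP |
|---|---|
| 70% | 1 − 0.20/0.30 = 33% |
| 50% | 1 − 0.20/0.50 = 60% |
| 25% | 1 − 0.20/0.75 = 73% |
| 0% | 1 − 0.20/1.00 = 80% |

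Below these shares the rule works. At 50% adherence with half the diary missing, the score is 1 − 0.5 × 0.5 = 75%, and a return count below 80% then excludes her.

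**4. Range around the even-spread assumption.** At 70% adherence there are 0.30 × 360 = 108 missed days. If the blank pages fall on missed days, 108 − 72 = 36 blank days (10% of exposure) are enough to keep her in. If every miss falls on a kept page, 108 are recorded and the diary score is 70%.

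**5. Effect on the PP difference, illustration only.** The documents give no rate of missing diaries. Assume a true difference of −2.0, an SC effect of 9.096 (the placebo-adjusted figure in SAP 3.1) and hence 7.096 for sMTS. Assume also that 5% of the affected arm's PP set is retained at half dosing, with effect proportional to dose. That arm's effect is multiplied by 1 − 0.05 × 0.5 = 0.975.
- Both arms: −2.0 × 0.975 = −1.95, a move of 0.05 towards non-inferiority.
- SC only: 7.096 − 9.096 × 0.975 = −1.77, a move of 0.23 towards it.
- sMTS only: 7.096 × 0.975 − 9.096 = −2.18, a move of 0.18 away from it.

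**The case against.** The strongest reply has five parts.

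- **A year without a diary is extreme.** The diary is reviewed at every treatment visit (Protocol Table 1, note 17), and Protocol 5.7 requires discrepancies to be discussed and recorded. This stands as a reason to expect few cases. It gives no rule for the gaps that remain.
- **The SAP never says that a blank day is a dose taken.** Correct: this is what the formula does by default. SAP 2.2 promises a Per-Protocol Memo before database lock that could define it. The memo's stated job is to show how the Appendix B criteria are programmed, and nothing commits it to a diary-completeness rule.
- **There are other exits from PP.** Item B.1 removes exposure under 90 days, and item D.1 removes any deviation with potential major impact on efficacy. Both stand. D.1 is a matter of judgement, and SAP 2.2 has the resulting list reviewed after lock, when the blinding described in SAP 1.2.3 has ended.
- **Two imperfect measures should agree before exclusion.** This is a fair choice when both are observed, and the fix keeps it.
- **SC may lack day-level dosing records.** SAP 4.3.3 describes a diary application time for patches only. However, subjects in both arms record local tolerance daily, before and after each dose (Protocol 6.6.3.2, SAP 4.6.4.2), which shows whether a page was kept.

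A reader might infer that any gap in the diary keeps a woman in PP however low her count. The table in the working shows otherwise. A reader might also infer that the PP estimate is pulled towards non-inferiority. The documents do not support that: under-dosing mainly in the sMTS arm moves it the other way.

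**Conclusion.** The point holds in limited form. On compliance grounds, a subject with wholly or largely missing diaries cannot be removed from PP, even with a pen or patch count well below 80%. This follows from the formula and the *both* rule alone. The one-third figure for a woman at 70% adherence also needs evenly spread misses, all recorded on kept pages.

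Separately, SAP 4.3.1 and Appendix B.2 can give different PP sets and must be reconciled whatever is decided about diaries.

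Among the efficacy analyses only PP is affected. The non-inferiority decision rests on the mITT population, which does not use compliance. The number of subjects concerned is unknown, so the shifts in step 5 of the working are not estimates. Their direction depends on which arm holds the retained under-dosed women. The change should still be made, because it is cheap and PP is offered as support for an open-label non-inferiority claim.

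**What to change.** Amend SAP 4.3.1 as follows, and repeat the same wording in Appendix B.2.

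1. Count a day as having a diary entry if it holds a dosing or local-tolerance record or a recorded miss. Compute diary compliance as (days with an entry − recorded misses) / days with an entry.
2. If entries cover less than a prespecified share of exposure days (for example 80%), treat diary compliance as missing and apply the 80% rule to the pen or patch measure alone.
3. Otherwise keep the rule that both measures must be below 80%.

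In the 70% example with one third of the diary missing, coverage is 67%, so the 70% return count decides and she is excluded.

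This does not alter the assumption of 100% compliance for a missing pen measurement or kit. The text should therefore also say how a subject is classified when neither measure is usable.

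The cost is SAP wording and a little programming on data already collected, and a slightly smaller PP set.

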5.1.2. Abaloparatide-SC

Abaloparatide-SC injection is supplied as a sterile, colorless, clear solution in a glass cartridge which is pre-assembled into a disposable single-use pen. The pen is intended to deliver 30 once daily abaloparatide doses of 80 μ g in 40 μ L of solution. Each pen contains 3120 μ g/1.56 mL.

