5.4.2. Abaloparatide-SC

Before use of abaloparatide-SC, subjects will perform a priming procedure after loading a new cartridge into the pen. Instructions for this procedure will be provided in a Pharmacy Manual. The contents of the medication cartridge will be inspected before each injection. If the cartridge contents are not clear and not colorless or if the cartridge contains visible particles, that cartridge will not be used and a new cartridge will be chosen.

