All abaloparatide-SC doses are to be given in the periumbilical region, rotating the site of injection each day. All abaloparatide-sMTS doses are to be applied on the thigh for 5 minutes. If it is deemed medically necessary for the study drug to be administered at an anatomic site other than what is required per protocol, the alternate site of study drug application/injection is to be recorded and the reason for change documented in the medical chart in the source documents as a protocol deviation.

Subjects will be dispensed abaloparatide-SC pens each month and will be instructed to use a new abaloparatide-SC injection pen after each 30-day period. A new set of abaloparatide-sMTS patches will be provided after each 30-day period. At each study site visit during the Treatment Period, the used and unused abaloparatide-SC injection pens and sMTS patches should be returned. All returned study drug should either be destroyed at the study site following that site's local procedures or sent to a depot identified by the Sponsor.

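### The SC pen formula makes no deduction for priming, so pen-based SC compliance reads too high, by an amount the documents do not state

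*SAP*

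**What the plan says.** SAP 4.3.1 gives two compliance calculations for the SC arm, one from diary-recorded missed doses and one from the drug left in returned pens. The pen version multiplies 45.5 mm by the number of used pens, subtracts the summed remaining lengths and divides by 1.08 mm. The SAP explains the starting length: "the 45.5mm is the initial measurement of unused study drug in an unused injection pen". For the divisor, its explanation is that "1.08mm is the distance the plunger travels for each 80 ug dose from the pen". Dividing by exposure days gives percent compliance.

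There is a separate branch for incomplete data: "If the measurement of drug remaining in any used pen is missing, then 100% compliance will be assumed" for the period that pen was meant to cover. That branch limits doses to the exposure duration. The complete-data formula has no such limit.

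On the pen itself, Protocol 5.4.2 states that "subjects will perform a priming procedure after loading a new cartridge into the pen", and adds: "Instructions for this procedure will be provided in a Pharmacy Manual". Protocol 5.6 says that subjects "will be instructed to use a new abaloparatide-SC injection pen after each 30-day period". Protocol 5.1.2 describes a pre-assembled disposable pen: "The pen is intended to deliver 30 once daily abaloparatide doses", each of 80 µg in 40 µL, and "Each pen contains 3120" µg in 1.56 mL.

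For the per-protocol (PP) population, SAP 4.3.1 excludes an SC subject on compliance grounds only when both calculations fall below 80%. SAP Appendix B lists compliance below 80% without naming a calculation. mITT is the primary efficacy population. PP is supportive.

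**The concern.** The starting length belongs to an unused pen, so on its face it is read before priming. Travel used up in priming then lies between the starting and remaining lengths, and the formula credits it as dosing. The error runs in one direction only and recurs with every new pen.

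Two outputs are at stake. The first is the SC compliance summaries, planned for the Safety, mITT and PP populations, by region and by antibody status. Every SC subject with measured pens contributes to these. The second is PP membership. An inflated pen value can hold a subject at or above 80% when her diary puts her below, and so keep her in PP. Retaining under-dosed SC subjects would, if it had any effect, tend to lower the SC mean in the PP repeat of the primary model, which is the direction that favours non-inferiority.

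**Working it through.** **Inputs**
- Starting length 45.5 mm per pen and 1.08 mm per dose (SAP 4.3.1).
- 30 intended doses per pen; 3120 µg in 1.56 mL; 80 µg in 40 µL (Protocol 5.1.2).
- A new pen every 30 days (Protocol 5.6) over 12 months of 30 days: 360 days and 12 pens.
- Priming travel: **not stated in either document**. Assumption: k dose-equivalents per pen, shown as a range.

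**Check of the plan's own figures.** Concentration: 3120/1.56 = 2000 µg/mL and 80/0.040 = 2000 µg/mL, so content and dose agree. Thirty dose strokes without priming use 30 × 1.08 = 32.4 mm and leave 13.1 mm. The formula returns (45.5 − 13.1)/1.08 = 30.0 doses. It is therefore correct when priming moves nothing.

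**With priming.** If D doses are truly taken, total travel is (D + 12k) × 1.08 mm and the formula returns D + 12k. The inflation is 12k/360 = 3.33k percentage points. A reading of 80% (288 doses) is reached at D = 288 − 12k.

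| k (assumed) | Inflation, points | Reading for a subject who takes every dose | True doses at a reading of 80% | True compliance |
|---|---|---|---|---|
| 0 | 0 | 100.0% | 288 | 80.0% |
| 0.25 | 0.8 | 100.8% | 285 | 79.2% |
| 0.5 | 1.7 | 101.7% | 282 | 78.3% |
| 1 | 3.3 | 103.3% | 276 | 76.7% |
| 2 | 6.7 | 106.7% | 264 | 73.3% |

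**One subject, 280 of 360 doses taken, k = 1**
- True compliance: 280/360 = 77.8%.
- SAP formula: (280 + 12)/360 = 81.1%.
- Priming deducted: (292 − 12)/360 = 77.8%.
- Exposure-duration cap only: min(292, 360)/360 = 81.1%.

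The deduction changes the 80% classification and the cap does not.

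**Missing-measurement branch.** Measured pens enter through the same expression. With one of 12 pens missing, the measured pens still add 11k doses: 11/360 = 3.1 points at k = 1, unless the cap at exposure duration applies. The missing pen is credited with up to 30 doses directly and carries no priming travel.

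**Effect on PP.** At k = 1 the pen formula changes membership only for an SC subject with diary compliance below 80% and true pen compliance from 76.7% to just under 80%. If her diary shows 80% or more, she stays in PP whatever the pen shows.

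**The case against.** The strongest objection is that the size cannot be established. The priming instructions are left to the Pharmacy Manual, and the device document in the SAP reference list is not available here. At a quarter of a dose per pen the shift is 0.8 points, and if priming moves no measurable length there is none. The priming text also speaks of loading a cartridge, whereas Protocol 5.1.2 describes a pre-assembled pen. All of this stands. It limits what can be said about size, but the formula still has no term for a step that the protocol requires.

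Several stronger readings are tempting and are not supported:
- **That each priming stroke counts as exactly one dose.** No volume is given; k = 1 is only one value in the range.
- **That the formula is uncapped throughout.** The missing-measurement branch is capped. Where the cap is absent, readings can exceed 100%, but no one crosses 80% because of it.
- **That only the SC arm can be inflated, so the cut-off is more lenient there.** The patch count credits every unreturned patch as delivered, and its complete-data formula is also uncapped. The net difference between arms cannot be derived.
- **That 45.5/1.08 = 42.1 doses, against 3120/80 = 39 by content, proves the error.** This compares plunger length with drug content. The documents do not say that 45.5 mm corresponds to the full 1.56 mL.
- **That the PP threshold itself drops to 76.7% or 73.3%.** The requirement that both calculations fall below 80% prevents this for anyone whose diary shows 80% or more.

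**Conclusion.** The defect is real and minor. If 45.5 mm is a pre-priming reading, as the SAP's description implies, pen-based SC compliance is overstated by 3.33 points per dose-equivalent of priming per 30-day pen. Over the assumed range of k from 0.25 to 2 this is 0.8 to 6.7 points, on 12 pens and 360 days.

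The clear consequence is in the SC compliance summaries. PP membership changes only for the narrow group with a low diary value and a true pen value in the gap. That group is probably small, but the documents do not allow a count. The primary mITT result does not depend on this calculation.

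**What to change.** 1. Confirm from the Pharmacy Manual or the cited device document that 45.5 mm is read before priming, and obtain the priming travel per pen. Check the 1.08 mm constant at the same time.
2. Subtract that travel once for each measured used pen before dividing by 1.08 mm, in both the complete-data and missing-measurement formulas. Pens credited by the missing-data rule need no deduction.
3. Reconcile Protocol 5.1.2 (pre-assembled pen) with Protocol 5.4.2 (loading a cartridge), so that it is clear when priming occurs.
4. Optional: apply the exposure-duration cap when all measurements are present, in both arms. This tidies the descriptive tables and leaves the 80% classification unchanged. Appendix B could also state that both calculations must be below 80%.

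The cost is one constant and one term in the formula. The Per-Protocol Memo and its programming specification, due before database lock, are the natural place for the PP part. No new data are needed.
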